7.2 Planned Analyses

Our primary hypothesis is that Chinese ESTEEM iCBT will yield significantly greater reductions in CAS and HIV risk behavior than weekly self-monitoring. Repeated measures intent-to-treat generalized linear mixed models (GLMM) with negative binomial distributions and maximum likelihood estimation will be fit to CAS at 4- and 8-month follow-up adjusted for baseline CAS with intervention arm as a covariate. We will test the best-fitting correlation structure, but based on our previous studies, expect it to be compound symmetrical. We will conduct exploratory analyses to determine within- and across-condition effects of each arm over time, including appropriate parameters for any trends evident over time. These models may be adjusted for any potential covariates (e.g., urban vs. rural residence; level of outness or education) that are associated with our outcomes if the intervention arms are not balanced on these variables.

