7.4 Data Coding

Data will be scored based on each measure's pre-specified ratings scale (see Measures packet on IRES). Outcomes utilized in statistical analyses will be continuous sum or mean scores, as applicable. Participant responses will be coded based on ratings of engagement and relevance of written responses to treatment content.

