Intervention	
1) ESTEEM iCBT: This online CBT treatment consists of 10 weekly modules that participants will complete over the course of 4 months. Modules contain weekly psychoeducational text and vignettes about minority stress and mental health; brief videos illustrating the CBT skills; and homework exercises that therapists review and provide feedback on. Homework exercises include weekly tracking of stress and mood, practicing new skills (e.g., mindfulness, cognitive restructuring), and exercises related to considering the origins of stress and negative emotions that participants may be experiencing. Therapists provide feedback after each homework assignment, including reviewing each participant's treatment goals as part of the first session's homework. Therapists who support this condition will be instructed to incorporate LGBTQ-specific content and feedback into homework reviews. This intervention was culturally adapted for Chinese YMSM and found to be acceptable and feasible.
 
2) Self-monitoring control: In this control condition, participants will be asked to indicate their past 7-day mood, stress experiences, and mental and behavioral health on an online survey. Participants will record these experiences once per week for 10 weeks.

Duration of Intervention	10 weekly modules in up to 17 weeks (four months)
Primary Outcome	Number of past-30-day condomless anal sex (CAS) acts with primary or casual partners as measured by the Timeline Follow-Back at the 8-month follow-up assessment.
Primary Analysis	We will examine the efficacy of the intervention using a generalized linear mixed model to test whether receipt of ESTEEM iCBT vs the self-monitoring control affects changes in the number of past-30 day CAS with primary or casual partners from baseline to 8-month follow up.

STATISTICAL ANALYSIS PLAN

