8.3 Analysis of Primary Outcome: HIV-Risk Behavior (Condomless Anal Sex)

Analysis	Primary analysis of primary outcome: Number of past-30-day condomless anal sex (CAS) acts with primary or casual partners as measured by the Timeline Follow-Back at the 8-month follow-up assessment.
Analysis population	All randomized participants
Endpoint	8-month follow-up
Unit of analysis	Participant
Method of analysis*	We will use repeated measures generalized linear mixed models with maximum likelihood estimation to test whether receipt of ESTEEM iCBT vs self-monitoring affects changes in the number of past-30-day CAS with primary or casual partners from baseline to 8-month follow up. We will use a contrast to test condition x time comparisons. We will test the best-fitting correlation structure, but based on our previous studies, expect it to be compound symmetrical. In the event of high skew or zero inflation, the appropriateness of modeling a negative binomial or Poisson distribution will be considered.
Handling of missing data	MAR assumption
Adjustment covariates	Adjustment for baseline covariates not balanced at randomization
Type I error	5% (2-sided)
Control of type I error	None

STATISTICAL ANALYSIS PLAN

Treatment effect estimate	Odds ratio with 95% confidence limits
---------------------------	---------------------------------------

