8.4.1 Analysis of Secondary Outcomes: HIV Risk Behavioral and Social-Cognitive Outcomes

Secondary HIV risk behavioral and social-cognitive outcomes at the immediate post-intervention timepoint (4-month follow-up) are: past-30-day condomless anal sex with main or casual partners, past-30 condomless anal sex with casual partners only, safer sex self-efficacy (SSQ), decisional balance for condom use (DBCUS), and past 4-month HIV/STI testing. Secondary outcomes at 8-month follow-up include: 30-day condomless anal sex with main or casual partners, past 30-day condomless anal sex with casual partners only, safer sex self-efficacy (SSQ), decisional balance for condom use (DBCUS), past 4-month HIV/STI testing history, HIV testing results, and syphilis testing results.

Analysis	In these models, we will assess whether ESTEEM iCBT will yield greater reduction in HIV risk behavioral and social-cognitive secondary outcomes at the immediate post-intervention (4-month follow-up) timepoint and the 8-month follow-up. HIV secondary outcomes include: past 30-day condomless anal sex with main or casual partners (TLFB), past 30-day condomless anal sex with casual partners only (TLFB), decisional balance for condom use (DBCUS), past 4-month HIV/STI testing, HIV testing results, and syphilis testing results.
Analysis population	All participants
Endpoint	Immediate post-intervention and 8-month follow-up
Unit of analysis	Participant
Method of analysis	Depending on the outcome we will use repeated measures generalized linear mixed models (for continuous outcomes) and generalized linear mixed models with a logit link (for binary outcomes). We will use maximum likelihood estimation with contrasts to test condition x time comparisons at each relevant timepoint. We will test the best-fitting correlation structure, but based on our previous studies, expect it to be compound

STATISTICAL ANALYSIS PLAN

	symmetrical. In the event of high skew or zero inflation, the appropriateness of modeling a negative binomial or Poisson distribution will be considered.
Handling of missing data	MAR assumption
Adjustment covariates	Adjustment for baseline covariates not balanced at randomization
Type I error	5% (2-sided)
Control of type I error	To control for the false discovery rate, we will apply a Bonferroni correction for each set of moderators (e.g., mental health, minority stress). Primary interpretation will focus on effect sizes.
Treatment effect estimate	Odds ratio with 95% confidence limits

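### SAP 8.3 reports a count primary outcome as an odds ratio and leaves open the negative binomial distribution that Protocol 7.2 fixes

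*SAP*

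**What the plan says.** **Effect measure.** SAP 8.3 defines the primary outcome as the number of past-30-day CAS acts with primary or casual partners at 8 months. The SAP Study Summary asks whether treatment "affects changes in the number of past-30 day CAS with primary or casual partners from baseline to 8-month follow up". The treatment-effect row of SAP 8.3 reads "Odds ratio with 95% confidence limits". The identical row stands in SAP 8.4.1 (counts, scales and binary test results), 8.4.2.1 (scale scores) and 8.4.3.1 (moderation, where a linear mixed model is specified). SAP 8.6 takes over the 8.4.2.1 approach for the exploratory scales. A logit link is named only in 8.4.1 and 8.4.2.1, and only for binary outcomes.

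**Distribution.** Protocol 7.2 is unconditional: "generalized linear mixed models (GLMM) with negative binomial distributions and maximum likelihood estimation will be fit to CAS" at 4 and 8 months, "adjusted for baseline CAS with intervention arm as a covariate". SAP 8.3 specifies a repeated-measures generalized linear mixed model with no distribution or link, and then: "We will use a contrast to test condition x time comparisons". On distribution it says only: "In the event of high skew or zero inflation, the appropriateness of modeling a negative binomial or Poisson distribution will be considered".

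**The concern.** A reader cannot produce the planned primary estimate from any model the SAP names for it. If a log-link coefficient were printed under the heading of an odds ratio, it would be read as the odds of any CAS, which is a different quantity.

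For the secondary outcomes this is more than a label. SAP 6.3 offers a focus on effect sizes as the guard against type I error, and 8.4.1, 8.4.2.1 and 8.4.3.1 repeat that focus. The effect size specified there does not exist for most of those outcomes.

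The open distribution is the part that can move the primary result. High skew has no cut-off, zero inflation has no test, and nothing says how Poisson and negative binomial are to be separated. The decision is therefore left to the analyst once the data are in hand.

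**Working it through.** **1. Which measures suit an odds ratio (SAP Table 1).**

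| Type | Measures | Number |
|---|---|---|
| Count | CAS with primary or casual partners; CAS with casual partners only | 2 |
| Scale score | SSQ, DBCUS, PHQ-9, GAD-7, AUDIT, DUDIT, SIDAS, three LGBIS subscales, DERS, MSPSS, LGBIS family support, RRS, ODSIS, OASIS, RSE | 17 |
| Testing history | Questionnaire; binary only if scored yes/no | 1 |
| Binary | HIV result, syphilis result | 2 |

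Total 2 + 17 + 1 + 2 = 22. The row suits 2, or 3 with testing history scored yes/no. It does not suit the other 19 or 20.

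**2. The effect measures are not interchangeable.** For a negative binomial count with mean *m* and dispersion *a*, P(0) = (1 + *am*)^(−1/*a*). The documents give no CAS mean or dispersion, so these inputs are assumed. Take a control mean of 4, *a* = 2 and a rate ratio of 0.60:
- Control: P(0) = 9^(−1/2) = 0.333, so P(any) = 0.667.
- Treated mean 2.4: P(0) = 5.8^(−1/2) = 0.415, so P(any) = 0.585.
- Odds ratio for any CAS = (0.585/0.415)/(0.667/0.333) = 0.70; mean difference = −1.6 acts.

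Over control means 2 to 6 and *a* from 1 to 4, a rate ratio of 0.60 corresponds to an odds ratio for any CAS of 0.60 to 0.79 and a mean difference of −0.8 to −2.4 acts.

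**3. Does the distribution matter for error?** From the documents: 60 per arm with 20% attrition, so 0.8 × 60 = 48 per arm, and a two-sided 5% test of condition by time from baseline to 8 months. Assumed: mean *m* of 2 to 4 acts, between-person gamma with shape 1, and extra visit-level gamma variation with shape *k*.

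In a Poisson mixed model with dispersion fixed at 1, the contrast is essentially a difference in log ratios of arm totals, with nominal variance equal to the sum of 1/total over the four arm-by-visit totals. Given the person means μ, the variance of each count is μ + μ²/*k*. With shape 1, E(μ²) = 2*m*², so the true variance exceeds the nominal one by the factor 1 + 2*m*/*k*. The true error is then 2[1 − Φ(1.96/√(1 + 2*m*/*k*))]. For *m* = 3 and *k* = 10 the factor is 1.6, 1.96/√1.6 = 1.55, and the error is 12.1%.

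| Visit shape *k* | Formula, *m* = 2 / 3 / 4 | Simulated, 20,000 null trials each |
|---|---|---|
| none | 5.0 / 5.0 / 5.0% | 4.9 / 5.3 / 5.3% |
| 20 | 7.4 / 8.6 / 9.8% | 7.2 / 8.3 / 9.6% |
| 10 | 9.8 / 12.1 / 14.4% | 9.6 / 11.9 / 14.5% |
| 4 | 16.6 / 21.5 / 25.8% | 15.6 / 21.0 / 25.6% |

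In the same simulations a marginal Poisson model with exchangeable correlation and estimated scale stays at 5.1-5.6%, and a Gaussian compound-symmetry model at 4.7-5.3%. Skew is 2.0 to 3.0 and the share of zeros 20-37%.

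**4. Do the error-controlling models agree?** Fitted models, mean 3, true rate ratio 0.70, about 1,000 trials per setting (Monte Carlo SE up to about 1.6 points):

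| Visit shape | Power: negative binomial | Power: scaled marginal Poisson | Power: Gaussian | Significance verdicts differ among the three |
|---|---|---|---|---|
| none | 49% | 51% | 44% | 11% |
| 10 | 38% | 35% | 30% | 11% |
| 4 | 29% | 26% | 22% | 14% |

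Under the null these three models reject in 4.2-5.7% of trials.

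**The case against.** - **The odds ratio is a template slip.** The identical row in four tables suggests carry-over, and correcting it changes no test. That is fair on the p-value. It remains the stated primary estimate, and it remains the effect size on which secondary interpretation is meant to rest.
- **SAP 8.3 does not name a Gaussian model.** This stands: Gaussian is an inference about what is fitted if the trigger is not met. The named alternatives, Poisson and negative binomial, do not give an odds ratio either. A zero-inflated or hurdle model would have an odds-ratio component, but none is named.
- **Protocol 7.4 is weak evidence on scoring.** Its sentence, "Outcomes utilized in statistical analyses will be continuous sum or mean scores, as applicable", refers to a measures packet not supplied, and read literally it would exclude the binary test results too. The count definition in the Study Summary and SAP 8.3 carries the point without it.
- **A footnote may be missing.** In SAP 8.3 the method-of-analysis label carries an asterisk with no note in the text available. If that note states a selection rule, the distribution point falls. The odds-ratio point rests on other rows of the table.
- **The simulations favour the concern.** Inputs are assumed, and the person shape is not varied. Skew of 2 to 3 would usually be called high, which makes Gaussian an unlikely final choice, yet the 11-14% disagreement includes it; disagreement between negative binomial and scaled Poisson alone was not computed. A competent check of fit should also reject dispersion-1 Poisson when overdispersion is marked. These limits stand. They argue for writing the check down.
- **Timing proves nothing.** The Study Summary was revised on 24 January 2023, after the planned end of data collection on 30 November 2022. The original SAP date is not visible, and nothing shows that anyone had seen data by arm. No inference about motive or order is drawn here.

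**Conclusion.** The concern holds. From the text alone, the primary effect measure does not match the outcome or any model named for it, and the mismatch extends to 19 or 20 of 22 measures. Also from the text, the SAP makes conditional and undefined a distribution that the Protocol states outright, subject to the unexplained asterisk.

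The size of the second part depends on assumed CAS means and dispersions. The material risk is one permitted choice, Poisson with dispersion fixed at 1: about 5% error with no visit-level overdispersion, 7-10% at shape 20, 10-15% at shape 10 and 16-26% at shape 4. The other choices keep the error near 5% but differ in power by roughly 7 to 8 points, and sometimes in the verdict.

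**What to change.** In SAP 8.3, fix the distribution as negative binomial with a log link, as in Protocol 7.2, and report the 8-month condition-by-time contrast as a rate ratio with 95% CI. List other distributions as named sensitivity analyses. If a fallback is wanted (for example for non-convergence), give an explicit rule applied blind to arm.

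Say which model form is primary. The SAP models change from baseline with a condition-by-time contrast; the Protocol models the 4- and 8-month values adjusted for baseline and names no such term. If the Protocol's form is chosen, define the 8-month arm rate ratio within it.

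In SAP 8.4.1, 8.4.2.1, 8.4.3.1 and, by reference, 8.6, replace the common row with mean differences (with standardised *d*) for scale scores, rate ratios for counts, and odds ratios only for binary outcomes. State how testing history is scored.

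The cost is SAP wording only; no new data are needed.

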8.4 Analysis of Secondary Outcomes

A similar approach will be taken for our secondary outcomes (i.e., depression, anxiety, and minority stress variables) as described in Section 8.3.

8.4.1 Analysis of Secondary Outcomes: HIV Risk Behavioral and Social-Cognitive Outcomes

Secondary HIV risk behavioral and social-cognitive outcomes at the immediate post-intervention timepoint (4-month follow-up) are: past-30-day condomless anal sex with main or casual partners, past-30 condomless anal sex with casual partners only, safer sex self-efficacy (SSQ), decisional balance for condom use (DBCUS), and past 4-month HIV/STI testing. Secondary outcomes at 8-month follow-up include: 30-day condomless anal sex with main or casual partners, past 30-day condomless anal sex with casual partners only, safer sex self-efficacy (SSQ), decisional balance for condom use (DBCUS), past 4-month HIV/STI testing history, HIV testing results, and syphilis testing results.

Analysis	In these models, we will assess whether ESTEEM iCBT will yield greater reduction in HIV risk behavioral and social-cognitive secondary outcomes at the immediate post-intervention (4-month follow-up) timepoint and the 8-month follow-up. HIV secondary outcomes include: past 30-day condomless anal sex with main or casual partners (TLFB), past 30-day condomless anal sex with casual partners only (TLFB), decisional balance for condom use (DBCUS), past 4-month HIV/STI testing, HIV testing results, and syphilis testing results.
Analysis population	All participants
Endpoint	Immediate post-intervention and 8-month follow-up
Unit of analysis	Participant
Method of analysis	Depending on the outcome we will use repeated measures generalized linear mixed models (for continuous outcomes) and generalized linear mixed models with a logit link (for binary outcomes). We will use maximum likelihood estimation with contrasts to test condition x time comparisons at each relevant timepoint. We will test the best-fitting correlation structure, but based on our previous studies, expect it to be compound

STATISTICAL ANALYSIS PLAN

	symmetrical. In the event of high skew or zero inflation, the appropriateness of modeling a negative binomial or Poisson distribution will be considered.
Handling of missing data	MAR assumption
Adjustment covariates	Adjustment for baseline covariates not balanced at randomization
Type I error	5% (2-sided)
Control of type I error	To control for the false discovery rate, we will apply a Bonferroni correction for each set of moderators (e.g., mental health, minority stress). Primary interpretation will focus on effect sizes.
Treatment effect estimate	Odds ratio with 95% confidence limits

8.4.2 Analysis of Secondary Outcomes: Mental Health, Minority stress Mechanisms, Universal Mechanisms

Secondary mental health, minority stress, and universal mechanisms will be assessed at the immediate post-intervention (4-month follow-up) timepoint and the 8-month follow-up. Secondary mental health outcomes include depression symptoms (measured by PHQ-9), anxiety symptoms (measured by GAD-7), alcohol and substance use (measured by AUDIT, DUDIT), and suicidality (measured by SIDAS). Secondary minority stress outcomes include concealment motivation (LGBIS), acceptance concerns (LGBIS), and internalized homonegativity (LGBIS). Secondary universal mechanism outcomes include emotion dysregulation (DERS), social support (MSPSS, LGBIS), and rumination (RRS).

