Secondary Outcomes	
Change from baseline to immediate post-intervention (4-month follow-up): Number of past-30-day CAS acts with primary or casual partners (TLFB), number of past-30-day CAS acts with casual partners (TLFB), safer sex self-efficacy (SSQ), decisional balance for condom use (DBCUS), past 4-month HIV/STI testing, depressive symptoms (PHQ-9), anxiety symptoms (GAD-7), alcohol use problems (AUDIT), drug use problems (DUDIT), suicidality (SIDAS), concealment motivation (LGBIS), acceptance concerns (LGBIS), internalized homonegativity (LGBIS), emotion dysregulation (DERS), social support (MSPSS), and rumination (RRS).
 
Change from baseline to 8-month follow up: Number of past-30-day CAS acts with only casual partners (TLFB), safer sex self-efficacy (SSQ), decisional balance for condom use (DBCUS), past 4-month HIV/STI testing, depressive symptoms (PHQ-9), anxiety symptoms (GAD-7), alcohol use problems (AUDIT), drug use problems (DUDIT), suicidality (SIDAS), concealment motivation (LGBIS), acceptance concerns (LGBIS), internalized homonegativity (LGBIS), emotion dysregulation (DERS), social support (MSPSS), rumination (RRS), HIV testing results, and syphilis testing results.

Exploratory Outcomes	
Change from baseline to immediate post-intervention (4-month follow-up): Depression severity and impairment (ODSIS), anxiety severity and impairment (OASIS), self-esteem (RSE).
 
Change from baseline to 8-month follow-up: Depression severity and impairment (ODSIS), anxiety severity and impairment (OASIS), self-esteem (RSE).

STATISTICAL ANALYSIS PLAN

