6.3 Power for Secondary Outcomes

Comparisons of in-person ESTEEM to waitlist have produced effect sizes of $d = .55$ for depression.²⁹ Average meta-analytic effects for depression ($d = .66$) of iCBT compared to weak control conditions also suggest that randomizing 120 participants provides a $\geq 80\%$ chance of detecting a significant difference ($p < .05$) between the conditions.³¹⁻³⁴ Given the number of secondary outcomes and to guard against Type 1 error, we will focus our results interpretation primarily on effect sizes rather than statistical significance.

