8.4.2.1 Mental Health, Minority stress Mechanisms, Universal Mechanisms

Analysis	In these models, we will assess whether Chinese ESTEEM iCBT will yield greater reduction in secondary outcomes (i.e., depression, anxiety, minority stress, and universal mechanisms) at the immediate post-intervention (4-month follow-up) timepoint and the 8-month follow-up. Mental health outcomes include depression symptoms (PHQ-9); Anxiety symptoms (GAD-7,); alcohol and substance use (AUDIT, DUDIT); and suicidality (SIDAS). Secondary minority stress outcomes include concealment motivation (LGBIS), acceptance concerns (LGBIS), internalized homonegativity (LGBIS). Secondary universal mechanism outcomes include emotion dysregulation (DERS), social support (MSPSS, LGBIS), and rumination (RRS).
----------	--

STATISTICAL ANALYSIS PLAN

Analysis population	All participants
Endpoint	Immediate post-intervention (4-month follow-up) and 8-month follow-up
Unit of analysis	Participant
Method of analysis	Depending on the outcome we will use repeated measures generalized linear mixed models (for continuous outcomes) and generalized linear mixed models with a logit link (for binary outcomes). We will use maximum likelihood estimation with contrasts to test condition x time comparisons at each relevant timepoint. We will test the best-fitting correlation structure, but based on our previous studies, expect it to be compound symmetrical. In the event of high skew or zero inflation, the appropriateness of modeling a negative binomial or Poisson distribution will be considered.
Handling of missing data	MAR assumption
Adjustment covariates	Adjustment for baseline covariates not balanced at randomization
Type I error	5% (2-sided)
Control of type I error	To control for the false discovery rate, we will apply a Bonferroni correction for each set of moderators (e.g., mental health, minority stress). Primary interpretation will focus on effect sizes.
Treatment effect estimate	Odds ratio with 95% confidence limits

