8.4.3.1 Moderation Analyses of Treatment Efficacy

Analysis	In these models, we will examine baseline depression (PHQ-9), anxiety (GAD-7), and minority stressors including concealment motivation (LGBIS), acceptance concerns (LGBIS), and internalized homonegativity (LGBIS) as potential moderators of
----------	---

STATISTICAL ANALYSIS PLAN

	ESTEEM iCBT efficacy, hypothesizing that YMSM with higher baseline depression, anxiety, and minority stress benefit most.
Analysis population	All participants
Endpoint	Immediate post-intervention (4-month follow-up) and 8-month follow-up
Unit of analysis	Participant
Method of analysis	
For all moderators (i.e., depression, anxiety, concealment motivation, acceptance concerns, and internalized homonegativity), a linear mixed model analysis will be performed. Moderation analysis models will include terms for condition, time, moderator, Condition X Time, Condition X Moderator, Time X Moderator, and Condition X Time X Moderator. To probe significant three-way interactions, we will perform simple slopes analyses and differences in slopes will be compared using z-score transformations.³⁵
 
We will test the best-fitting correlation structure, but based on our previous studies, expect it to be compound symmetrical. In the event of high skew or zero inflation, the appropriateness of modeling a negative binomial or Poisson distribution will be considered.

Handling of missing data	MAR assumption
Adjustment covariates	Adjustment for baseline covariates not balanced at randomization
Type I error	5% (2-sided)
Control of type I error	To control for the false discovery rate, we will apply a Bonferroni correction for each set of moderators (e.g., mental health, minority stress). Primary interpretation will focus on effect sizes.
Treatment effect estimate	Odds ratio with 95% confidence limits

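### The multiplicity rule for the secondary outcomes is written over sets of moderators, which those models do not contain, so it cannot be applied as it stands

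*SAP*

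**What the plan says.** SAP 8.4.1 (HIV-risk behavioral and social-cognitive outcomes) and 8.4.2.1 (mental health, minority stress and universal mechanisms) share one template. Each sets a 5% two-sided type I error. Each describes the test in the same way: "We will use maximum likelihood estimation with contrasts to test condition x time comparisons at each relevant timepoint". Each fills the error-control row with the same sentence. In 8.4.1 it contains the words "we will apply a Bonferroni correction for each set of moderators (e.g., mental health, minority stress"; in 8.4.2.1 it opens "To control for the false discovery rate, we will apply a Bonferroni correction for each set of moderators". In both it is followed by a remark that interpretation will rest mainly on effect sizes.

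The sentence appears a third time in 8.4.3.1, the moderation table. There it fits: "For all moderators (i.e., depression, anxiety, concealment motivation, acceptance concerns, and internalized homonegativity), a linear mixed model analysis will be performed". Those five moderators fall into the two example sets.

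Section 6.3 recognises that there are many secondary outcomes and says that, "to guard against Type 1 error, we will focus our results interpretation primarily on effect sizes rather than statistical significance". Section 8.6 sends the exploratory outcomes through the approach of 8.4.2.1, so they inherit the same row.

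The text of 8.4.1 also says: "Secondary outcomes at 8-month follow-up include: 30-day condomless anal sex with main or casual partners". Sections 4.1 and 8.3 make that same measure at 8 months the primary endpoint, and 8.3 gives its error control as none.

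**The concern.** A Bonferroni rule needs a family and a count. In 8.4.1 and 8.4.2.1 the family is sets of moderators, and there are none, so the divisor is undefined. Anyone carrying out the plan must either leave every secondary contrast at 5% or choose a family themselves, possibly with the data in hand. In either case a report could say that a Bonferroni correction was pre-specified, and nominal secondary findings would look better protected than they are.

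Two smaller matters add to the uncertainty. The row names the false discovery rate as its target but uses a procedure designed for the family-wise rate, so the intended error rate is unclear. And 8-month condomless anal sex (CAS) with main or casual partners falls under two error rules, one as primary and one as secondary.

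**Working it through.** **1. The plan's own figure.** Section 6.3 claims at least 80% power at p < .05 for d = .66 with 120 randomized. A two-sample t-test, two-sided 5%, gives 0.948 with 60 per arm and 0.893 with 48 per arm (60 less the 20% attrition of Section 6.2). The figure reproduces, at an unadjusted 5% per test.

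**2. Counting the secondary contrasts.**

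| Domain | 4 months | 8 months | Total |
|---|---|---|---|
| HIV risk | 5 | 6 | 11 |
| Mental health | 5 | 5 | 10 |
| Minority stress | 3 | 3 | 6 |
| Universal mechanisms | 3 | 3 | 6 |
| **Study Summary** | **16** | **17** | **33** |

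Section 4.2 adds the LGB-specific family support subscale at two timepoints: 33 + 2 = 35. Section 8.4 also repeats the 8-month primary endpoint: 35 + 1 = 36.

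**3. Literal reading: no moderators, so each test is at 5%.** Under the global null with k independent tests, the chance of at least one false positive is 1 − 0.95^k:

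- k = 33: 1 − 0.95^33 = 0.816; expected false positives 33 × 0.05 = 1.65
- k = 35: 0.834; 1.75
- k = 36: 0.842; 1.80

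The outcomes are correlated, and the documents give no correlations. With 200,000 simulated sets of 33 equicorrelated z-tests:

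| Assumed common correlation | Chance of at least one false positive |
|---|---|
| 0 | 0.82 |
| 0.1 | 0.80 |
| 0.3 | 0.69 |
| 0.5 | 0.53 |
| 0.7 | 0.35 |

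**4. Charitable reading: moderators is a slip for outcome domains.** Mental health and minority stress are also outcome domains, so this is plausible. The rule still lacks a count:

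- HIV risk (all of 8.4.1) and universal mechanisms are not named as sets.
- Whether the two timepoints form one family is not stated. For mental health this means 5 tests (0.05/5 = .01) or 10 tests (0.05/10 = .005). The t-test power for d = .66 with 48 per arm is 0.726 at .01 and 0.640 at .005, against 0.893 at .05.
- Membership in 8.4.1 is inconsistent: the text includes safer sex self-efficacy, and the table's Analysis row leaves it out.

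**5. What a by-domain rule would deliver.** With 5% control in each of four independent domains, the chance of any false positive across all four under the global null is up to 1 − 0.95^4 = 0.185.

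**The case against.** The best defence has four parts.

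*The intent may be recoverable.* The two example sets are also outcome domains, and the examples are not presented as a complete list. Bonferroni within outcome domain may be what was meant. This stands as far as it goes: a reader might infer that the plan certainly leaves every secondary test uncorrected, and the documents do not establish that. What they establish is that the rule as written has no family in these tables, and that the likely intended meaning still gives no count.

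*82% is a ceiling.* It assumes independence, whereas most measures are tested at two timepoints and several are closely related (PHQ-9 with GAD-7, the three LGBIS minority-stress subscales, the two CAS counts). This also stands, so the range should be quoted. Across the correlations assumed, the figure stays well above 5%.

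*Bonferroni does control the false discovery rate.* This is correct, because that rate never exceeds the family-wise rate. A reader might infer that the procedure is invalid for its stated target. It is only conservative for it; the wording leaves the target unclear.

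*Effect sizes come first.* Sections 6.3, 8.4.1 and 8.4.2.1 say so, there is one primary endpoint, and the objective is preliminary efficacy. This limits the consequence. It sets no threshold, though, and the same tables keep 5% two-sided tests and 95% limits. Had effect sizes been meant to replace correction, the row could have read none, as it does in 8.3.

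The double listing of 8-month CAS is a slip that the rest of the SAP resolves: the Study Summary and Section 4.2 list it as secondary at 4 months only. It needs deleting but adds no weight to the main point.

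**Conclusion.** The concern holds in this form: the error-control rule in 8.4.1 and 8.4.2.1 cannot be applied as written, because it is defined over moderators that those models do not contain. Read literally, 33 contrasts (35 or 36 by other sections of the SAP) run at 5% each, with a chance of at least one false positive of 82% under independence and roughly 35% to 80% at assumed common correlations of 0.7 to 0.1. Those figures rest on the global null and on correlations that the documents do not supply. Read charitably, the family size is still open, and for mental health the choice moves power at d = .66 from about 73% to 64%.

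The effect is confined to the interpretation of secondary outcomes and, through Section 8.6, exploratory ones. The primary analysis and its conclusion are not affected.

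**What to change.** - **Family.** In 8.4.1 and 8.4.2.1, replace the reference to moderators with each outcome domain (HIV risk, mental health, minority stress, universal mechanisms), counting the 4- and 8-month contrasts together. Reconcile the Study Summary, Section 4.2 and Section 8.4 lists so that each domain has one stated number of tests.
- **Procedure.** Use one that matches the stated target: Benjamini-Hochberg at 5% within domain if the false discovery rate is meant, or Holm if family-wise control is meant. Holm is never less powerful than the Bonferroni rule now named.
- **Scope.** State that control is within domain, and that the chance of any false positive across the four domains is up to about 18.5% under independence.
- **Moderation.** Keep the moderator wording only in 8.4.3.1.
- **Primary endpoint.** Delete 8-month main-or-casual CAS from the 8.4.1 secondary list.
- **Exploratory outcomes.** State in 8.6 whether they are adjusted or unadjusted.

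Declaring the secondary tests unadjusted would also remove the ambiguity, but it would abandon the correction that the SAP says it intends.

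The cost is SAP wording and a column of adjusted p-values; no new data are needed. The downside is that some nominally significant secondary results will not survive adjustment.
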